7.3.3 Disease Characteristics

Disease characteristics will be summarized (based on Section 7.1) including:

- Baseline platelet count (see Section 4.3.1 for definition)
- Baseline platelet count category ($\leq 15 \times 10^9/L$, $> 15 \times 10^9/L$ to $< 30 \times 10^9/L$)
- Number and percentage of subjects with any bruising or bleeding
- WHO bleeding scale at baseline (a response of "No" is equivalent to Grade 0). If multiple bleeding events are reported at baseline, the worst (most severe) will be chosen as baseline.

Grade 0	No bleeding
Grade 1	Petechial bleeding
Grade 2	Mild blood loss (clinically significant)
Grade 3	Gross blood loss
Grade 4	Debilitating blood loss

Number and percentage of subjects with any surgery

Disease characteristics will be listed for the Full Analysis Set.

7.3.4 Medical History

Medical history will be coded using MedDRA version 23.0 or higher.

The frequency and percentage of subjects experiencing any medical conditions will be tabulated by System Organ Class (SOC) and Preferred Term (PT). If a PT or SOC was reported more than once for a subject, the subject will be counted once in the incidence for that PT or SOC.

Medical history will be listed for the Full Analysis Set.

7.3.5 Prior and Concomitant Medications

All medications will be coded using Anatomical Therapeutic Chemical (ATC) classification based on World Health Organization (WHO) Drug Dictionary (March 2020, B3 or higher). The coding version may be updated prior to database lock if a newer version is available.

Prior medications are medications taken and stopped prior to first dose of study drug.

Concomitant medications during the Core Phase are medications being taken on or after the first dose of study drug in the randomized control period and prior to the first dose of the study drug in the Open Label Extension period.

Medications that start before the first dose of study drug in the randomized control period and continue into the randomized control period will be considered as concomitant medications for the Core Phase.

Concomitant medications for the Open Label Extension period are those which begin prior to the open label extension period and continue into the Open Label Extension period or those which start on or after the first day of study treatment in the Open Label Extension period.

Medications that begin in the Core Phase and have missing end dates are assumed to be

concomitant medications in both Core Phase and Open Label Extension Phase.

The number and percentage of subjects who have taken prior or concomitant medications will be summarized by ATC Level 2 Category and Preferred Name. A subject will be counted only once for medications taken more than once.

Rescue therapy may include:

- The addition of any new ITP medication or medication to treat thrombocytopenia, such as:
 - Corticosteroids ATC level 2: CORTICOSTEROIDS FOR SYSTEMIC USE
 - IVIg ATC level 2: IMMUNE SERA AND IMMUNOGLOBULINS
 - Anti-D Preferred Term: Anti-D (rh) immunoglobulin
 - Platelet transfusion Concomitant Procedure
- Any increase in the Day 1/Visit 2 dose of a concomitant ITP medication

TPO-RAs are not allowed as rescue therapy.

The following summary will be provided:

- Concomitant medications by study phase (Core Phase and Open Label Extension Phase)
- Concomitant Medications taken as rescue for a bleeding event by study phase (Core Phase and Open Label Extension Phase)
- Rescue Therapy used by study phase (Core Phase and Open Label Extension Phase)

Prior and concomitant medications will be listed for the Full Analysis Set.

7.3.6 Prior and Concomitant Procedures

Prior procedures are procedures performed prior to first dose of study drug.

Concomitant procedures during the Core Phase are procedures being performed on or after the first dose of study drug in the randomized control period and prior to the first dose of the study drug in the Open Label Extension period.

Concomitant procedures for the Open Label Extension period are those which start on or after the first day of study treatment in the Open Label Extension period.

Prior and concomitant procedures will be listed for the Full Analysis Set.

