5.3 Stopping Criteria

Subjects may be removed from the Core Phase and directly enrolled into the open-label Extension Phase due to a lack of treatment effect.

A lack of treatment effect will be defined as:

- Platelet count remains <30×10⁹/L after more than 3 weeks at the maximum dose of study drug per Table 4. Subjects may also be terminated from the Core Phase and directly enrolled into the Extension Phase after 7 days of therapy at the maximum dose if they have dangerously low platelet counts (in the opinion of the Investigator), or
- Subjects who require rescue therapy more than 3 times or continuous rescue therapy for more than 3 weeks (Section 8.6).

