ⁱ For females of childbearing potential. A pregnancy test should be performed every 3 months during Visit E-3, Visit E-6, Visit E-9, Visit E-12, Visit E-15, Visit E-18, Visit E-21, Visit E-24, and Visit E-25.

^j Study drug should be administered with food. Administer study drug in clinic during Visit E-1, E-6, Visit E-12, and Visit E-18 in order to confirm proper administration technique.

Sobi, Inc. Clinical Study Protocol AVA-PED-301

Visit	E-1 ^a	E-2	E-3	E-4	E-5	E-6	E-7 – E-24	E-25
Day	1	30 (±7 Days)	60 (±7 Days)	90 (±7 Days)	120 (±7 Days)	150 (±7 Days)	Every 30 Days (±7 Days)	720 (±7 Days)
Review Administration Instructions and Provide to Subject	X	X	X	X	X	X	X	
Dispense Dosing Diary	X	X	X	X	X	X	X	
Retrieve Unused Medication and Record Compliance	X	X	X	X	X	X	X	X
Adverse Events ^k	X	X	X	X	X	X	X	X
Prior/Concomitant Medications	X	X	X	X	X	X	X	X

^k Adverse events (AEs) should be recorded from the time the subject/subject's legally authorized representative (LAR) signs the informed consent/assent.

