4. DEFINITIONS AND CONVENTIONS FOR DATA HANDLING

4.1 Study Periods

Study periods are defined as follows:

Screening Period: Starting the day of signature of informed consent up to and including the day before randomization. For subjects who are not randomized, the screening period will end on the day the subject is determined to be a screen failure.

Randomized Control Period / **Core Phase**: Starting the day of randomization up to Visit 14 or the day of study drug discontinuation.

Follow-up Period in Core Phase: Starting the day after last dose of study drug in the Core Phase up to 30 days (±7 days) following the last dose of study drug in the Core Phase (only for subjects not entering the open label extension period).

Open Label Extension Period: Starting the day of Visit E-1/Day 1 to early termination or end of study. Visit 14 and Visit E-1 occur on the same day, and as a result are part of both the Randomized Control Period and the Open Label Extension Period.

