7.5.2 Adverse Events

Adverse events (AEs) will be coded using MedDRA version 23.0 or higher and will be classified by SOC and PT of MedDRA. The coding may be updated according to newly released versions of the dictionary. Severity of AEs will be graded according to Common Terminology Criteria for Adverse Events (CTCAE) v5.0.

A treatment emergent adverse event (TEAE) is defined as any AE that occurs after administration of the first dose of study drug.

AEs are classified as related or not related to the study drug based on investigator assessment. AEs with missing or unknown relationship to the study drug will be considered as related AEs.

TEAEs with starting date prior to the first dose date in the Open Label Extension Phase will be classified as TEAEs in the Core Phase. TEAEs with starting date on or after the first dose date in the Open Label Extension Phase will be classified as TEAEs in the Open Label Extension Phase. An overall summary of TEAEs will be provided for each phase and the entire study including:

• Any TEAE

- Any related TEAE
- Any Grade 3-5 TEAE
- Any TEAE leading to study discontinuation
- Any TEAE leading to drug withdrawn
- Any TEAE leading to dose reduction/interruption
- Any serious TEAE
- Any serious TEAE by relationship to study drug (related, unrelated)
- Any death
- Any AESI (AE of special interest) (Thromboembolic events, CTCAE Grade ≥3 Bleeding events)

The following events will be tabulated and summarized. The output will be sorted by decreasing frequency of PT within SOC which is sorted alphabetically in overall events.

- TEAEs by SOC and PT
- TEAEs by PT
- Drug-related TEAEs by SOC and PT
- Drug-related TEAEs by PT
- TEAEs by maximum toxicity grade, SOC and PT
- TEAEs leading to study discontinuation by SOC and PT
- Serious TEAEs by SOC and PT
- Drug-related serious TEAEs by SOC and PT
- AESIs by AESI category and PT

Two categories for Adverse Events of Special Interest (AESI) will be summarized and are defined based on terms in Standardized MedDRA Queries (SMQs) from MedDRA v26.1 or later:

- Thromboembolic events Any thrombotic or embolic event, whether arterial or venous SMQ = Embolic and thrombotic events
- Bleeding Events Any clinically significant blood loss [e.g., bleeding events with CTCAE grade 3+ (based on AE severity [AESEV]>=3] - SMQ = Haemorrhage terms (excl laboratory terms)

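### Adverse events dated on the switch day go to the Extension even if they precede the first open-label dose, and the phase rules for switch-day rescue overlap with no stated precedence

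*SAP*

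**What the plan says.** **The shared day.** SAP 4.1 states: "Visit 14 and Visit E-1 occur on the same day, and as a result are part of both the Randomized Control Period" and the Extension. Protocol 4.1.2 has open-label dosing begin at E-1, and Table 8 footnote j (Protocol Appendix A) says "Administer study drug in clinic during Visit E-1, E-6, Visit E-12, and Visit E-18". Under Protocol 1.5.4 and 9.1.15, the platelet count at this visit decides the open-label starting dose.

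**Adverse events (SAP 7.5.2).** "TEAEs with starting date on or after the first dose date in the Open Label Extension Phase will be classified as TEAEs" of the Extension; those with an earlier start date belong to the Core. The split is by date and exclusive.

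**Medications (SAP 7.3.5).** Core medications are those taken "prior to the first dose of the study drug in the Open Label Extension period". Extension medications are those carried over from before, plus "those which start on or after the first day of study treatment in the Open Label Extension period".

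**Procedures (SAP 7.3.6).** Core procedures are "procedures being performed on or after the first dose of study drug in the randomized control period and prior to the first dose" of open-label drug. For the Extension: "Concomitant procedures for the Open Label Extension period are those which start on or after the first day of study treatment" in that period. SAP 7.3.5 identifies platelet transfusion as rescue through the procedure data, so it follows this rule.

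**End of the Core.** SAP 4.1 ends the Core at Visit 14 or on the day study drug is discontinued. Protocol 8.1 asks for dates of medication administration and does not mention clock times.

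**The concern.** The switch day holds pre-dose observations that belong to randomised treatment: laboratory draw, examination, vital signs, bleeding assessment and platelet count. A rule that works on dates alone cannot separate them from what follows the first open-label dose.

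For AEs, the consequence is misattribution by rule. SAP 7.1 analyses the Extension by cohort and overall, not by Core arm. A placebo child's pre-dose event would thus leave the placebo column and appear only as an event on open-label avatrombopag. SAP 7.5.3 summarises Core laboratory values by visit, so the same abnormality could appear in the Core laboratory table but as an Extension AE.

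For rescue, the issue is an unresolved boundary. Protocol 5.3 lets a child move directly to open label when counts are judged dangerously low. That judgement is close to the one that permits rescue in Protocol 8.6, and rescue with immunoglobulin, steroids or platelets is not among the Extension exclusions in 6.2.2. Rescue on the exit day is therefore foreseeable. The Core rescue proportion is a tested secondary endpoint within the step-down procedure.

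**Working it through.** **1. Apply each rule to an event on the E-1 date, before the first open-label dose.**

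| Event | Core rule met? | Extension rule met? | Result by the text |
|---|---|---|---|
| AE (7.5.2) | No: start date is not before the dose date | Yes | Extension only |
| Rescue drug (7.3.5) | Yes: before the dose | Yes: on the first day | Both |
| Transfusion (7.3.6) | Yes: before the dose | Yes: on the first day | Both |

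If programming compares dates only, with no times, the last two rows become Extension only. SAP 4.3 uses date and time for baseline; the phase rules name no time field.

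**2. Early exits.** SAP 4.1 does not say whether the exit visit lies inside the Core. Table 7 footnote b expects the last Core dose one day before Visit 14. If the same pattern holds at an early exit, and discontinuation is read as the last-dose day, rescue at the exit visit falls after the Core has closed.

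**3. How early this can arise.** Dosing starts at Level 4 (Table 4). Under Table 3 the level can rise at Week 2 and again two weeks later, so Level 6 is reached at 2 + 2 = Week 4. The 7-day exit in Protocol 5.3 can then occur at about 4 + 1 = Week 5.

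**4. Who is exposed on rescue.** A child who exits for more than three rescues, or for continuous rescue beyond three weeks, has already been rescued in the Core and cannot become never rescued. That leaves children who exit on the platelet criterion with no earlier rescue, and any child whose first rescue falls at Visit 14 before the dose.

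**5. Size for rescue.** The plan gives no rescue rates, so there is no figure to reproduce; its power statements are not in dispute. Group sizes are 54 and 18 (SAP 2.2). One child moves the proportion by 1/18 = 5.6 points on placebo and 1/54 = 1.9 points on avatrombopag.

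The p-values below are two-sided Fisher tests on **assumed** counts. With total rescues t fixed, P(x) = C(54,x)·C(18,t−x)/C(72,t), and p is the sum of all P(x) no larger than that observed.

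| Avatrombopag | Placebo, true | One moved | Two moved | Three moved |
|---|---|---|---|---|
| 8/54 | 8/18: p=0.019 | 7/18: p=0.044 | 6/18: p=0.099 | – |
| 4/54 | 5/18: p=0.038 | 4/18: p=0.101 | – | – |
| 4/54 | 8/18: p=0.001 | 7/18: p=0.004 | 6/18: p=0.013 | 5/18: p=0.038 |

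At moderate effects, one or two children decide significance. At a large effect, three do not.

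**6. Size for AEs.** Table 7 schedules on-treatment central laboratory draws and examinations at Visits 6, 10 and 14, so the switch visit is one of three for each. This is a share of assessments, not of AEs. A finding detected at Visit 14 may have an earlier onset date, and 7.5.2 uses onset.

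**7. Primary endpoint.** SAP 7.4 makes exit before Week 10 a non-response and excludes counts from the rescue start date onward. Neither step depends on which phase the rescue is filed under.

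**The case against.** A reader might infer that the SAP files switch-day rescue to the Extension instead of the Core, so that a rescued child counts as never rescued. The documents do not support this. The Core sentences in 7.3.5 and 7.3.6 capture anything before the first open-label dose, 7.3.5 lets a medication sit in both phases, and 4.1 places Visit 14/E-1 in both periods. Loss requires a programming choice that the text does not demand. This part of the objection stands.

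Several further points also carry weight:

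- No sentence makes 7.3.5 or 7.3.6 the derivation of the rescue endpoint, which SAP 7.4 words as rescue during the 12 Core weeks.
- The case report form is not among the documents, so silence on times in Protocol 8.1 does not prove that times are not collected.
- No passage expressly says that an early-exit visit is also the first open-label dosing day, though direct enrolment makes it plausible.
- The planned test is CMH with Fisher as fallback, and the rescue counts above are chosen, not estimated.
- Nor can one say which later test would be blocked. SAP 7.4 starts the sequence at the key secondary endpoint and does not expressly say that the rest follows table order.
- If exits are mainly on placebo, lost rescues would understate the drug's benefit.

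None of this reaches the AE rule, which is exclusive and by date as written. Nor does it supply a precedence rule for the overlap between first dose and first day.

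**Conclusion.** The point holds in two parts of different strength. The AE part is literal: an event with onset on the E-1 date before the open-label dose leaves the randomised comparison and is reported as an open-label avatrombopag event, whichever arm the child was in. How many such events will occur cannot be estimated from the documents.

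The rescue part is an ambiguity. By the text a pre-dose rescue belongs to the Core, but a date-only or exclusive derivation, or one that closes the Core at the last Core dose, would drop it. Each placebo child lost moves the endpoint by 5.6 points. Whether that changes a conclusion depends on rescue counts that the documents do not give. That exits will be mostly on placebo is an assumption, in line with the planning durable response rates of 41.3% and 3.4%. The primary endpoint is essentially unaffected. The wording should be settled before unblinding, so that the placement of a possibly decisive rescue is not chosen afterwards.

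**What to change.** State one precedence rule in SAP 7.3.5, 7.3.6 and 7.5.2 for events dated on E-1:

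- Rescue medication and transfusions count as Core unless recorded as starting after the first open-label dose.
- AEs with onset at the pre-dose laboratory draw, examination or vital signs of Visit 14/E-1 count as Core under the same proviso. Other AEs dated that day stay in the Extension.
- The Core rescue endpoint includes the Visit 14 day or the early-exit visit day.

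The AE rule should not rely on WHO bleeding grades, because SAP 5.1 says they are not linked to individual AEs.

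The cost is a few sentences and one derivation, with no change to trial conduct. The documents describe no field tying an AE to a laboratory draw or examination, so AEs dated on E-1 may need a blinded listing review before lock. A small downside is that some rescues given later the same day without a recorded time will be attributed to the Core.

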7.4 Efficacy Analysis

Unless otherwise stated, all primary and secondary efficacy endpoints defined in Section 3.2.1 will be analyzed for the FAS and PPS.

For the efficacy evaluation of the platelet count responses, platelet counts assessed by local labs will be used. Platelet counts collected via the central lab will be used in the safety assessments of

clinical laboratory tests.

The methods used for efficacy analysis for the Core Phase are summarized in Error! Reference source not found.3. All Cochran-Mantel-Haenzel (CMH) tests at alpha=0.05 within each age cohort will be performed adjusting for baseline platelet count category ($\leq 15 \times 10^9 / L \text{ vs} > 15 \times 10^9 / L$). For the CMH test in the overall group, the test will be performed adjusting for age cohort and baseline platelet count category. Fisher's exact test will be used if the number of durable platelet responders is spare in the strata (less than 3 in a specific subgroup). Durable platelet response with 2-sided 95% exact binomial (Clopper-Pearson) confidence interval (CI) will be provided. The difference in response rate (avatrombopag – placebo) with 2-sided 95% CI (Wald) will also be provided.

Subjects without sufficient data for the determination of response status (i.e., responder versus non-responder) will be treated as non-responders in the analysis.

For the primary efficacy endpoint determination, a subject must have remained in the Core phase through at least Week 10 (to have at least 6 weeks of platelet count data starting from week 5 to either week 12 if the subject completes the core phase or the last week if the subject prematurely terminates the core phase). If a subject terminates the Core phase prior to Week 10, they would be considered a non-responder for the primary efficacy endpoint.

Endpoint	Analysis Method
Primary Efficacy Endpoint	
Durable platelet response defined as proportion of subjects achieving at least 6 out of 8 weekly platelet counts $\geq 50 \times 10^9 / L$ during the last 8 weeks of the 12 week treatment period in the Core Phase in the absence of rescue medication. In the case of rescue medication being used, platelet count assessments from the start date of rescue medication up until 4 weeks after the end date of rescue medication will be excluded from analysis.	CMH test
Alternative Primary Efficacy Endpoint • Platelet response defined as proportion of subjects for whom at least 2 consecutive platelet assessments are ≥50×10 ⁹ /L during last 8 weeks of the 12 week treatment in the Core Phase in the absence of rescue medication	CMH test

Secondary Efficacy Endpoints

Percentage of weeks subjects have a platelet count $\geq 50 \times 10^9 / L$ during 12 weeks of treatment in the Core Phase, in the absence of rescue therapy. Denominator for this calculation is based on the number of weeks the subject was on treatment (up to 12 weeks)

CMH test

tests

Nonparametric

Wilcoxon Rank Sum

Platelet response at Day 8 (defined by the proportion of subjects with a platelet count $\geq 50 \times 10^9 / L$ at Day 8, in the absence of rescue therapy)

Endpoint	Analysis Method
• Percentage of weeks subjects have a platelet count between ≥50×10 ⁹ /L and ≤150×10 ⁹ /L, during 12 weeks of treatment in the Core Phase, in the absence of rescue therapy. Denominator for this calculation is based on the number of weeks the subject was on treatment (up to 12 weeks)	Nonparametric Wilcoxon Rank Sum tests
• Proportion of subjects who require rescue medications during 12 weeks of treatment in the Core Phase of the study	CMH test
• Overall incidence and incidence of severe bleeding symptoms (scale 3 and 4) associated with ITP measured using the WHO Bleeding Scale	CMH test
Exploratory Efficacy Endpoint	
• Month 3 durable platelet response defined as the proportion of subjects achieving at least 3 out of 4 weekly platelet counts ≥50×10 ⁹ /L during the last 4 weeks of the 12 week Treatment Period in the Core Phase in the absence of rescue medication	CMH test

Note: Fisher's exact test will be used if CMH test fails.

If the test of the treatment effect on the primary efficacy endpoint is statistically significant, the statistical tests on the secondary efficacy endpoints will be considered inferential; otherwise, the tests will be considered descriptive and no statistical inference can be drawn with regards to the secondary efficacy endpoints.

To control the family-wise Type I error rate at a significance level of $\alpha = 0.05$ (2-sided), a step-down closed testing procedure will be used when testing the secondary efficacy endpoints. Starting with the key secondary efficacy endpoint, if the test is significant at $\alpha = 0.05$, then the test on the next endpoint will be considered inferential; otherwise, the tests on the subsequent endpoints will be considered descriptive only. This process will be repeated from the top of the hierarchy for the remaining endpoints.

The efficacy variables collected during the Open Label Extension Phase will be summarized descriptively.

For the Core Phase, observed values and change from baseline over time for platelet counts will be summarized. For the Core Phase, WHO bleeding scale will be summarized by visit.

For the Extension phase, observed values for platelet counts and WHO bleeding scale will be summarized by visit.

Blood product transfusions will be summarized for both the Core Phase and the Open Label Extension Phase including the following variables:

- Number and percentage of subjects with at least one blood product transfusion
- Total number of blood product transfusions
- Type of blood product
- Reasons for transfusion
- Number of packs/units per transfusion

Platelet count and blood transfusions will be listed for the Full Analysis Set.

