11.2.2 Efficacy Analysis

All efficacy analyses will be conducted using the FAS, unless otherwise specified.

In order to satisfy the primary endpoint requirements of different regulatory agencies, 2 primary efficacy endpoints will be evaluated. Two separate SAPs will be developed to describe the statistical methodology for the analysis of each primary efficacy endpoint. In the first SAP, the endpoint described as "Primary Efficacy Endpoint" in Section 3.1 will be assessed as the primary efficacy endpoint, and the endpoint described as the "Alternative Primary Efficacy Endpoint" in Section 3.2 will be assessed as the first secondary efficacy endpoint. In the second SAP, the endpoint described as "Alternative Primary Efficacy Endpoint" in Section 3.2 will be assessed as the primary efficacy endpoint, and the endpoint described as the "Primary Efficacy Endpoint" in Section 3.1 will be

assessed as the first secondary efficacy endpoint. Both SAPs will evaluate the additional secondary efficacy endpoints described in Section 3.3.

For the efficacy evaluation of the platelet count responses, platelet counts assessed by local labs will be used. Platelet counts collected via the central lab will be used in the safety assessments of clinical laboratory tests.

Primary Efficacy Endpoint:

The primary efficacy endpoint is the durable platelet response as defined by the proportion of subjects achieving at least 6 out of 8 weekly platelet counts $\geq 50 \times 10^9 / L$ during the last 8 weeks of the 12 week Treatment Period in the Core Phase, in the absence of rescue medication. The null hypothesis is that the treatment effect of avatrombopag is the same as that of placebo. The alternative hypothesis is that the treatment effect of avatrombopag is different than that of placebo.

The primary efficacy endpoint will be tested between avatrombopag and placebo using the Cochran-Mantel-Haenszel 2-sided test at α =0.05, adjusting for age cohort and Baseline platelet count (\leq 15×10⁹/L vs >15×10⁹/L), or the Fisher's exact test, when data is sparse. In addition, the numbers and percentages of responders in each treatment group, the associated 95% confidence intervals (CI), and the 95% CI for the difference between avatrombopag and placebo will be summarized. The primary analysis will be performed based on the FAS and repeated on the PPS as a supportive analysis. Other sensitivity analyses of the primary efficacy endpoint may be performed as appropriate.

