2. STUDY DESIGN

2.1 Summary of Study Design

AVA-PED-301 is a multi-center, randomized, double-blind, placebo-controlled, parallel-group study in pediatric subjects with a 12 week Core Phase followed by a 2-year open-label Extension Phase to evaluate the efficacy, safety, tolerability, and PK/PD profile of avatrombopag, as well as to provide data on palatability/acceptability, dosing parameters, and response to treatment.

The study will enroll at least 72 pediatric subjects, aged ≥ 1 to <18 years (Figure 1). Subjects will be assigned to 3 age cohorts in a 2:2:1 ratio and subjects will be randomized within each cohort in a 3:1 ratio to receive either avatrombopag or placebo. Subject age at the time of randomization will be used. Cohort 1 and Cohort 2 will each enroll more subjects than will be enrolled in Cohort 3 in order to minimize the exposure of the youngest age group to placebo. Randomization will be stratified by age cohort. Subjects will also be stratified by an average baseline platelet count of $\leq 15 \times 10^9/L$ or $>15 \times 10^9/L$ to $<30 \times 10^9/L$ in order to ensure treatment groups are approximately balanced.

[figure not shown]
Enrollment into the Core Phase will be staggered by descending age cohort.

- Cohort 1: \ge 12 to \le 18 years (n = 21 avatrombopag; 7 placebo)
- Cohort 2: \geq 6 to <12 years (n = 21 avatrombopag; 7 placebo)
- Cohort 3: ≥ 1 to ≤ 6 years (n = 12 avatrombopag; 4 placebo)

All available PK and safety data through Week 10 of the Core Phase will be reviewed by the Sponsor and/or the Sponsor's designee (e.g., for unblinded PK data) for the first 10 subjects enrolled into Cohort 1 prior to opening enrollment into the Core Phase for subjects in Cohort 2. Likewise, all available PK and safety data through Week 10 will be reviewed by the Sponsor and/or the Sponsor's designee (e.g., for unblinded PK data) for the first 10 subjects enrolled into Cohort 2, prior to opening enrollment into the Core Phase for Cohort 3. As the study progresses and more data become available, the PK/PD model will be updated with emerging data in order to confirm the appropriate dose of avatrombopag in each cohort. Enrollment will not stop in the current cohort for the data review after Week 10, or for the data review after each cohort is fully enrolled. The dose of avatrombopag may be modified during the study based on results of the PK and safety data

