2.2 Sample Size Determination

The proposed sample size is based on the anticipated response rates for avatrombopag and placebo for the primary endpoint (durable response) and the key secondary endpoint (platelet response for 2 consecutive weeks).

Based on the eltrombopag PETIT2 study conducted in pediatric patients with chronic ITP, the durable response rates were 41.3% and 3.4% for eltrombopag and placebo, respectively (Grainger, 2015). It is reasonable to assume that the treatment effect of avatrombopag will be very similar to that of eltrombopag, due to both drugs being in the same class, having similar mechanisms of action, and treating similar patient populations (e.g., patients aged ≥ 1 to <18 years with relapsed or refractory disease after 1 or more previous treatments for ITP and a Baseline platelet count $<30\times10^9$ /L). With the 3:1 ratio of avatrombopag to placebo, a total of 72 subjects (54 avatrombopag and 18 placebo) will provide at least 90% power to detect a treatment difference of 37.9% in durable response at α =0.05, based on the Fisher's exact test.

In addition, a 12 week study of romiplostim in treating pediatric ITP patients showed that 88% of romiplostim treated subjects achieved a platelet count $\geq 50 \times 10^9 / L$ for 2 consecutive weeks (key secondary endpoint), whereas none of the placebo treated subjects achieved the same endpoint (Bussel, 2011). With the 3:1 ratio of avatrombopag to placebo, a total of 72 subjects (54 avatrombopag and 18 placebo) will provide $\geq 99\%$ power to detect a treatment difference of 80% in proportion of subjects achieving a platelet count $\geq 50 \times 10^9 / L$ for 2 consecutive weeks at $\alpha = 0.05$, based on the Fisher's exact test.

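### The SAP prescribes alpha=0.05 tests within each age cohort without giving them a status; for durable response they have about 2-9% power in Cohort 3 and 28-44% in Cohorts 1 and 2, so they should become descriptive estimates with suitable intervals.

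*SAP*

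**What the plan says.** SAP section 7.4 prescribes two levels of testing. The overall CMH test adjusts for age cohort and baseline platelet category. In addition, "All Cochran-Mantel-Haenzel (CMH) tests at alpha=0.05 within each age cohort will be performed adjusting for baseline platelet count category". Fisher's exact test replaces CMH "if the number of durable platelet responders is spare in the strata (less than 3 in a specific subgroup"), and a note to the efficacy table adds that Fisher is used if CMH fails. Response rates get Clopper-Pearson intervals and the difference gets a Wald interval. SAP section 7.1 has Core Phase analyses produced for each cohort as well as overall.

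The multiplicity paragraphs of section 7.4 begin "To control the family-wise Type I error rate at a significance level of" 0.05. They cover the primary endpoint and then the secondary endpoints in order. Cohort tests are not placed in that order, adjusted, or called descriptive. The introduction to SAP section 7 treats every analysis in the plan as a priori.

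Protocol section 11.2.2 specifies only an overall "Cochran-Mantel-Haenszel 2-sided test" adjusted for cohort and platelet category. SAP section 5.1, which lists changes from the protocol, does not mention cohort tests. SAP section 2.2 gives power only for all 72 subjects. Section 2.1 gives Cohorts 1 and 2 21 avatrombopag and 7 placebo subjects each, and Cohort 3 "n = 12 avatrombopag; 4 placebo", kept small to limit placebo exposure in the youngest children.

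**The concern.** A prespecified test with a stated alpha invites a verdict of significant or not significant. In a trial spanning ages 1 to <18 years, where the youngest cohort also takes a different formulation, readers will look at the cohort results. If the test in Cohort 3 can hardly succeed even when the drug works as planned, p>0.05 there says almost nothing, yet it can be read as missing efficacy in that age group. No planned analysis asks whether the effect differs by age, so nothing else in the SAP corrects that reading. The interval planned beside the test matters too, because it is the natural substitute once the test is set aside.

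**Working it through.** **Inputs.** From SAP section 2.2: "the durable response rates were 41.3% and 3.4% for eltrombopag and placebo, respectively", 54 vs 18 subjects overall, and "at least 90% power to detect a treatment difference of 37.9% in durable response" by Fisher's test. From SAP section 2.1: cohort sizes 21:7, 21:7 and 12:4. The test is two-sided at 0.05. Assumptions, because the documents give no figures: the same response rates in every cohort and in both platelet strata, and a stratum split between 50/50 and about 75/25.

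**Method.** Power = sum over all (x, y) of Bin(x; n1, 0.413) × Bin(y; n2, 0.034) × [test significant at (x, y)]. The stratified CMH power uses the same sum over two platelet strata, without continuity correction.

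**Step 1, the plan's own figure.** For 54 vs 18, Fisher's test gives 94.5%. The stated power of at least 90% reproduces.

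**Step 2, power by cohort for durable response.**

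| Cohort | Fisher | Stratified CMH |
|---|---|---|
| 1 and 2, each (21 vs 7) | 28.1% | 43.8-44.3% |
| 3 (12 vs 4) | 1.7% | 8.1-8.8% |

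Ignoring the platelet strata would give 42.1% and 15.9%, but that is not the test the SAP names. Which column applies depends on the sparse-data rule. If fewer than 3 responders is counted per arm, Fisher applies almost always, since 4 or 7 placebo subjects at 3.4% rarely yield 3 responders. If it is counted per cohort, CMH nearly always stands. If it is counted per platelet stratum, simulation at splits from 50/50 to about two thirds/one third gives 38-41% and 5-6%, inside the range.

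**Step 3, what significance requires by Fisher with no placebo responder.**
- Cohort 3: 8/12 gives p=0.077 and 9/12 gives p=0.019, so 9 are needed; 12 × 0.413 = 5.0 are expected.
- Cohorts 1 and 2: 9/21 gives p=0.062 and 10/21 gives p=0.030, so 10 are needed; 21 × 0.413 = 8.7 are expected.

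**Step 4, all three cohorts together.**
- Fisher: 0.281² × 0.0169 = 0.0013, so at least one cohort has p>0.05 in 99.9% of trials.
- Stratified CMH (50/50 split): 0.440² × 0.0879 = 0.017, so 98.3%.

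**Step 5, the other main endpoint.** At 80% vs 0% for two consecutive counts, Cohort 3 power is 79% (Fisher) to 94% (stratified CMH), and Cohorts 1 and 2 exceed 99.9%.

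**Step 6, the planned Wald interval.** Take 5/12 vs 0/4, about the expected Cohort 3 result.
- Wald: the difference is 0.417 and SE = √(0.417 × 0.583/12 + 0) = 0.142, because 0/4 contributes no variance. The interval is 0.417 ± 1.96 × 0.142 = 0.14 to 0.70. Fisher gives p=0.245 on the same data.
- Newcombe: the Wilson limits are 0.193 to 0.680 for 5/12 and 0 to 0.490 for 0/4. The lower limit is 0.417 − √(0.224² + 0.490²) = −0.12 and the upper limit is 0.68.

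Enumerated over all Cohort 3 outcomes at the planning rates, the Wald interval covers the true difference in 88% of trials (87.5%) and excludes zero in 81%, while Fisher is significant in 2%. Newcombe covers in 96%. With no effect and a common response rate of 20%, 30% or 40%, Wald coverage in Cohort 3 is 79%, 77% and 82%.

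**Step 7, an exact homogeneity test as an alternative.** Expected placebo responders number 18 × 0.034 = 0.6, and P(none) = 0.966^18 = 54%. With none, the exact conditional test of a common odds ratio has only one possible table and p=1.

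**The case against.** The primary objective, the protocol's test and the power statement all concern the whole trial, and no passage makes a claim depend on a cohort test. Much of what one would want by cohort is already planned: rates with exact intervals, and a difference with an interval. That stands. It makes this a point about labelling, interval choice and a view of consistency, not about the primary conclusion.

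Three stronger readings are tempting, and the documents do not support them.

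- *The cohort tests raise the claimed 5% error rate.* They do not. The claim in section 7.4 covers the primary endpoint and the step-down sequence, and a cohort test neither opens nor closes any step. Taken as a separate family, three unadjusted tests have a nominal chance of 1 − 0.95³ = 14.3% of at least one false positive. For a null endpoint with 20-40% events, the unstratified asymptotic test gives 8-14% and Fisher about 6%. None of this is error in the controlled sequence.
- *Every cohort test is underpowered.* Step 5 shows otherwise for two consecutive counts at the assumed 80% vs 0%.
- *The plan would declare the drug ineffective in an age group.* The SAP says nothing of the kind. The chance in step 4 is of p>0.05, and the point estimate may still favour the drug.

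**Conclusion.** The point holds for durable response. The cohort tests carry an explicit alpha but no stated role, and their power is about 28-44% in Cohorts 1 and 2 and 2-9% in Cohort 3. With a uniform effect at the planning rates, at least one cohort would show p>0.05 in 98% or more of trials. This rests on 41.3% vs 3.4% applying at every age and in both platelet strata, and on the assumed stratum splits; the conclusion is the same for both tests and for each reading of the sparse-data rule. The overall test, the step-down sequence and the primary conclusion are untouched. The planned interval does not repair the cohort results, because in Cohort 3 it is too narrow and often contradicts the test beside it. The change is modest, but it alters what is reported by age.

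**What to change.** In SAP section 7.4:

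1. Remove the alpha=0.05 tests within cohorts, or state that any cohort p-value is nominal and descriptive and supports no claim.
2. Report each cohort's response rates, and their difference with a score interval (for example Newcombe) or an exact interval in place of Wald.
3. Show consistency across cohorts descriptively, for example with a forest plot of the three differences and the overall one. Do not rely on an exact test of homogeneity of the odds ratio, which is uninformative in about 54% of trials at the planning rates.
4. List the by-cohort efficacy analyses in section 5.1 as an addition to the protocol.

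The cost is SAP wording and some table programming; sample size, data collection and the primary analysis do not change. The downside is that there is no formal p-value per age group and the cohort intervals are wider: in the 5/12 vs 0/4 example, 0.80 wide (−0.12 to 0.68) against 0.56 (0.14 to 0.70).
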